5. SUBJECT SELECTION AND WITHDRAWAL

5.1 Inclusion Criteria

- Adult (18 years or older) patients, with any solid tumor type, of all racial and ethnic origins
- Undergoing lumbar puncture for clinical or radiographic suspicion of leptomeningeal metastasis
- Provide study-specific informed consent
- Patients with unequivocal or suspicious MRI findings.
- Of those with a definitive diagnosis of LM (i.e. positive CSF cytology), 10 evaluable patients will be accrued.

5.2 Exclusion Criteria

- Prior CSF fluid which identified malignant cells after 10 evaluable patients with positive CSF are accrued.

5.3 Inclusion of Women and Minorities

Women of all races and ethnic groups are eligible for this trial.

5.4 Subject Recruitment

Patients with solid tumors who are undergoing lumbar puncture for suspicion of leptomeningeal metastasis will be screened by the treating clinical staff for eligibility. Upon providing informed consent, we will be notified so that preparations can be made for study inclusion. Clinical research coordinators

**Columbia University Medical Center
Herbert Irving Comprehensive Cancer Center**

will be allowed to consent study patients.

At the time of obtaining consent, consent will be requested for blood tests to check peripheral blood CTC's and circulating DNA (2 tubes, 10 cc mL each), as well as consent for additional CSF from subsequent taps, to be performed if clinically indicated, usually in the setting of an initially negative tap.

Patient visits, lumbar punctures, CSF collection, clinical evaluation and data reporting will take place at Columbia University Medical Center. CSF collection from 46 eligible breast cancer subjects is estimated to take approximately 24 months.

Study Calendar

	Pre-Enrollment	Lumbar Puncture (LP) #1	LP #2 (if clinically indicated, i.e. previously negative tap)	LP #3 (if clinically indicated, i.e. previously negative tap)	Clinical Follow-up (2 and 6 month after LP #1)
Informed Consent	X				
Inclusion/Exclusion	X				
Standard Cytologic Assessment (CSF)		X	X	X	
OncоЗEE (CSF)		X	X	X	
OncоЗEE (peripheral blood)		X	X	X	
Assess Report of Metastatic Tumor (or Primary, if not available) – ER/PR/HER2, if breast cancer, as well as mutational profile for solid tumors		X			
Patient Status (unequivocal vs. suspicious for LM)	X				X ^a

^a Patients will be followed at two additional time periods after LP #1: 2 (+/- 1 month) and 6 months (+/- 1 month) after LP #1. The goal of this is to determine LM status: unequivocal vs. suspicious and whether this changes over time (i.e. suspicious to unequivocal). If the patient is not able to come in, communication with the patient over the phone is acceptable (but not ideal).

5.5 Early Withdrawal of Subjects

5.5.1 When and How to Withdraw Subjects

Patients may elect to withdraw from the study at any time by informing the Principal Investigator or Sub-Investigator.

5.5.2 Data Collection and Follow-up for Withdrawn Subjects

As this protocol does not involve any change in standard of care being delivered to the patients, no additional follow up is required for patients who elect to withdraw consent.

**Columbia University Medical Center
Herbert Irving Comprehensive Cancer Center**

Each patient who consents to participate in the study will be assigned a unique study ID. The Principal Investigator or Sub-Investigator will collect pertinent data for each patient on Case Report Forms (CRFs). Information collected will include: demographic, pathologic, radiographic and specimen collection data.

6. ADVERSE EVENTS: LIST AND REPORTING REQUIREMENTS

6.1 Adverse events

This protocol does not require any additional tissue sample collection than that which would be standard of care, except for the additional tube of CSF collected during standard collection procedures during routine investigation of LM. Experimental data from this research will not influence the therapeutic decisions. The treating physician will not be informed of the result. The rate of adverse events is expected to be very low.

Risk will primarily be attributed to the additional CSF required for the study; withdrawing excess amounts of CSF can induce nausea, positional headache or light headedness.

6.1.1 Unanticipated Problem

An unanticipated problem is any incident, experience or outcome involving risks to subjects or others in any human subjects research that meets all of the following criteria:

- Unexpected (in terms of nature, severity or frequency) given (a) the research procedures that are described in the IRB-approval protocol and informed consent document, and (b) the characteristics of the subject population being studied;
- Related or possibly related to participation in such research (e.g., there is a reasonable possibility that the incident, experience or outcome may have been caused by the procedures involved in such research); and
- Suggests that the research places subjects or others at a greater risk of harm (including physical, psychological, economic or social harm) than was previously known or recognized.

6.2 Recording of Adverse Events

As this trial is not an interventional/therapeutic study, we will not be recording adverse events. Only events qualifying as UPs will be reported to the CUMC IRB according to institutional policy/procedures.

7. DATA REPORTING / REGULATORY REQUIREMENTS

7.1 Data Collection

The Herbert Irving Comprehensive Cancer Center has an electronic clinical trials and data management system that will be used for data collection. CRFs for the study will be built into Velos for data entry. The system has full auditing capabilities which is web-based and housed on a server in a fully HIPAA compliant server room with restricted access and video camera monitoring. All users must login with their own application username and password. Users off campus must first access the Virtual Private

Columbia University Medical Center Herbert Irving Comprehensive Cancer Center

Network with their assigned campus username and password and then use their application credentials. Users are only able to see study information if they are indicated as study personnel in our electronic IRB system. Users are limited to access based on the role assigned in their corresponding protocol. Subject data is entered directly into the system, which (in the case of Columbia subjects) confirms the correct identity of patients via an interface with the electronic medical patient index. Staff with the appropriate IRB defined roles can run reports within the system for reporting purposes.

7.2 Quality Control and Quality Assurance

The PI and study team will perform routine quality reviews to ensure the protocol is being executed in compliance with the IRB approved procedures.

7.3 Confidentiality

Information about study subjects will be kept confidential and managed according to the requirements of the Health Insurance Portability and Accountability Act (HIPAA). Those regulations require a signed subject authorization informing the subject of the following:

- What protected health information (PHI) will be collected from subjects in this study
- Who will have access to that information and why
- Who will use or disclose that information
- The rights of a research subject to revoke their authorization for use of their PHI.

In the event that a subject revokes authorization to collect or use PHI, the investigator, by regulation, retains the ability to use all information collected prior to the revocation of subject authorization. For subjects that have revoked authorization to collect or use PHI, attempts should be made to obtain permission to collect at least vital status (e.g., that the subject is alive) at the end of their scheduled study period.

The subject binders will be maintained with in the CPDM offices, a secured floor within the Herbert Irving Pavilion and only the investigator and study staff will have access to the file.

7.4 Source Documents

Source data is all information, original records of clinical findings, observations, or other activities in a clinical trial necessary for the reconstruction and evaluation of the trial. Source data are contained in source documents Examples of these original documents, and data records include: hospital records, clinical and office charts, laboratory notes, memoranda, subjects' diaries or evaluation checklists, pharmacy dispensing records, recorded data from automated instruments, copies or transcriptions certified after verification as being accurate and complete, microfiches, photographic negatives, microfilm or magnetic media, x-rays, subject files, and records kept at the pharmacy, at the laboratories, and at medico-technical departments involved in the clinical trial.

7.5 Case Report Forms

The study case report form (CRF) is the primary data collection instrument for the study. All data requested on the CRF must be recorded. All missing data must be explained. If a space on the CRF is

**Columbia University Medical Center
Herbert Irving Comprehensive Cancer Center**

left blank because the procedure was not done or the question was not asked, write “N/D”. If the item is not applicable to the individual case, write “N/A”.

7.6 Records Retention

Records relating to a specific research activity, including research records collected by investigators, must be maintained for at least three years after completion of the research (45 CFR 46.115(b); 21 CFR 56.115(b); 21 CFR 312.62). This minimum retention period applies whether or not any subjects were enrolled in the study.

If the research is FDA regulated, records should be retained for at least two years after approval of the investigational agent by FDA; if it is not approved, records should be retained at least two years after the study is terminated and FDA is notified (note the additional requirement below for clinical research studies);

Clinical records, including consent forms that document clinical intervention or clinical diagnostic procedure research-related procedures, must be retained in medical records by the institution for at least seven years, per CUMC and NYP policy which is based on state law.

8. STATISTICAL CONSIDERATIONS

8.1 Study Design/Endpoints

CSF cytopathologic analysis is the gold standard in providing diagnostic confirmation of LM, but is associated with a relatively low sensitivity (approximately 50% on the first lumbar puncture) and is highly examiner-dependent. Repeat, multi-site and high volume lumbar punctures are often required, which may increase sensitivity up to 90% [7], but are associated with complications, treatment delays, and patient discomfort. We anticipate that using OncoCEE will result in a 25% improvement in the sensitivity to detect leptomeningeal metastasis vs. standard cytopathologic analysis on the first lumbar puncture (75% vs. 50%). We will have 80% power to detect this difference on the first lumbar puncture in 36 evaluable patients (two-sided alpha, 0.05) in patients with unequivocal or suspicious findings radiographically or clinically for LM. No false positives are assumed with this method, as seen with pilot data in peripheral blood (A.3). With this population, we anticipate that the prevalence of LM, defined as positive CSF cytopathologic analysis on lumbar puncture at any time point, will be approximately 90% (i.e. 32 out of 36 patients). In addition, we will accrue evaluable 10 patients with positive CSF fluid to compare OncoCEE in patients with definitive LM. Thus, the total sample size for the study will be 46 patients.

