Official Title: Pilot study evaluating the utility of OncoCEETM (Cell Enrichment and Extraction) technology, a novel immunocytochemical microfluidic device, in the diagnosis of leptomeningeal metastasis (LM) from solid tumors through identification of circulating tumor cells (CTCs) in cerebrospinal fluid (CSF)

Unique Protocol ID: AAAQ4761

Registration Identifier: NCT02948751

Document Date: July 17, 2018

Columbia University Medical Center
Herbert Irving Comprehensive Cancer Center

TITLE Pilot study evaluating the utility of OncoCEE™ (Cell Enrichment and Extraction) technology, a novel immunocytochemical microfluidic device, in the diagnosis of leptomeningeal metastasis (LM) from solid tumors through identification of circulating tumor cells (CTCs) in cerebrospinal fluid (CSF).

PRINCIPAL INVESTIGATOR

[name], MS
Assistant Professor of Medicine
Columbia University Medical Center
[contact]
E-mail: [contact]

[name]
Assistant Professor of Neurology
Columbia University Medical Center
[contact]
E-mail: [contact]

FUNDING AGENCY

NIH R03 (1 R03 CA208547-01)
Biocept, Inc

Protocol Synopsis

Title	Pilot study evaluating the utility of OncoCEE™ (Cell Enrichment and Extraction) technology, a novel immunocytochemical microfluidic device, in the diagnosis of leptomeningeal metastasis (LM) from solid tumors through identification of circulating tumor cells (CTCs) in cerebrospinal fluid (CSF).
Short Title	Microfluidic device to diagnose leptomeningeal metastasis in solid tumors
Study Duration	Approximately 24 months
Study Center(s)	Single center
Primary Objectives	Determine whether the microfluidic device will demonstrate a greater sensitivity for the detection of leptomeningeal metastasis (LM) in solid tumors as compared to standard cytopathologic analysis
Number of Subjects	46
Diagnosis and Main Inclusion Criteria	Patients with solid tumors who are undergoing lumbar puncture for suspicion of leptomeningeal metastasis
Statistical Methodology	We anticipate that using OncoCEE will result in a 25% improvement in the sensitivity to detect leptomeningeal metastasis vs. standard cytopathologic analysis on the first lumbar puncture (75% vs. 50%). We will have 80% power to detect this difference on the first lumbar puncture in 36 evaluable patients with unequivocal or suspicious findings (two-sided alpha, 0.05). In addition, we will accrue 10 patients with positive CSF fluid to compare OncoCEE in patients with definitive LM.

**Columbia University Medical Center

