2.2 Secondary Objective(s)

- Assess the feasibility of determining estrogen, progesterone and HER2 receptor status for breast cancer patients on the CSF CTCs collected by OncoCEE™ technology
- Assess concordance between the receptor status of the primary and/or metastatic breast tumor, and that of the leptomeningeal cells collected by OncoCEE™ technology
- Explore characteristics of the CTCs and cell free DNA collected from CSF and compare them to CTCs and cell free DNA collected simultaneously from peripheral blood. Examples include BRAF mutations in melanoma and EGFR mutations in non-small cell lung cancer.
- Explore the performance of OncoCEE™ technology and standard cytopathology in diagnosing LM within 2 subgroups: patients with unequivocal MRI findings of the CNS and those with suspicious MRI findings of the CNS
- Explore the yield of checking for CSF CTCs and cell free DNA from CSF in individuals who have had an initial negative LP by standard cytopathologic and CTC analysis, for whom an additional LP is otherwise clinically warranted

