4. STUDY DESIGN

4.1 General Design

This study will prospectively enroll 36 evaluable subjects with solid tumors who are undergoing workup for clinical suspicion of leptomeningeal metastasis (LM) for unequivocal or suspicious findings by imaging or clinical determination. Neuroimaging consisting of MRI of the brain or total spine (or both, as clinically indicated) will be obtained in all patients. Patients will also undergo a lumbar puncture and standard CSF evaluation, which may consist of intracranial pressure measurement, CSF protein, glucose, white and red cell analysis, infectious cultures, as well as conventional cytopathologic analysis (cytocentrifuge). An additional CSF sample will be obtained for evaluation of CSF CTCs by OncoCEE™ technology and cell-free DNA (recommended amount: 1 tube, 10 mL) at the time of lumbar puncture.

We will define LM as previously described [14]. Patients will be considered to have a definitive diagnosis of LM if they have a positive CSF cytology.. We will accrue 10 patients with positive cytology. Unequivocal MRI findings will be defined as leptomeningeal enhancement with subarachnoid nodules, enhancement in basal cisterns, or enhancement/clumping of nerve roots. Findings such as multiple superficial brain metastases, intraventricular masses, dural enhancement associated with epidural metastasis, or new hydrocephalus will be considered suspicious but nondiagnostic. Patients with unequivocal or suspicious findings on imaging or clinical findings (without known CSF positivity) will be eligible for this study (n=36).

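### Is the 80% power undermined because it is quoted for 36 patients when about 32 are expected to have LM, with no paired test or discordance stated?

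*Combined protocol and SAP*

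**What the plan says.** Section 8.1 sets first-puncture sensitivity at 50% for cytology and 75% for OncoCEE, and states: "We will have 80% power to detect this difference on the first lumbar puncture in 36 evaluable patients (two-sided alpha, 0.05"). The Protocol Synopsis repeats it: "We will have 80% power to detect this difference on the first lumbar puncture in 36 evaluable patients with unequivocal or suspicious findings".

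Section 8.1 then says how common LM should be in this cohort: "defined as positive CSF cytopathologic analysis on lumbar puncture at any time point, will be approximately 90% (i.e. 32 out of 36 patients"). It also assumes that OncoCEE yields no false positives. It cites repeat or high-volume puncture as a means "which may increase sensitivity up to 90% [7"]. A further 10 patients with known positive fluid bring the total to 46; the power statement does not cover them.

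Section 4.1 shows that the comparison is within patient. Cytology is done at the lumbar puncture, and "An additional CSF sample will be obtained for evaluation of CSF CTCs by" OncoCEE at that same puncture. Section 4.1 also admits patients whose imaging findings "will be considered suspicious but nondiagnostic". Repeat punctures are not scheduled for everyone. Section 5.4 has them "to be performed if clinically indicated, usually in the setting of an initially negative tap", and Section 2.2 limits them to patients "for whom an additional LP is otherwise clinically warranted".

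No section names the primary test, gives a discordant share, or says how 36 relates to 32.

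**The concern.** Three things look wrong at first reading.

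- **Denominator.** Sensitivity is a proportion of patients with LM. If power was computed on 36 and only 32 contribute, it is overstated.
- **Pairing.** With both assays on the same patient, 75% and 50% do not fix the power. It also depends on how often cytology is positive when OncoCEE is negative, and the plan gives no such figure.
- **Optimism.** LM means cytology-positive at some time point. An ever-positive rate of 90% needs nearly every patient to have LM and repeat cytology to work at the top of its cited range, although repeat punctures depend on clinical indication and some patients enter on suspicion only.

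This is the only justification for the 36. If the true power were well below 80%, a null result could be misread as strong evidence against a 25-point gain.

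**Working it through.** **Inputs from Section 8.1:** sensitivities 0.75 and 0.50, so d = 0.25; two-sided alpha 0.05; 36 patients; 32 with LM. **Assumed, because the documents give no value:** s, the share of LM patients positive on cytology and negative on OncoCEE. The OncoCEE-only share is then 0.25 + s, and total discordance is psi = 0.25 + 2s.

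**1. Can the plan's figures be reproduced?** Take a one-sample normal test of 75% against a fixed 50%, using the null variance: power = Phi(0.25·√n / 0.5 − 1.96).

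- n = 31: 79.5%
- n = 32: Phi(2.828 − 1.96) = 80.7%

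So 32 is the smallest n that reaches 80%, and 32/0.9 = 35.6 rounds up to 36. Every input is in Section 8.1. This is one plausible origin; the plan does not state it. The route treats cytology's 50% as known, and its exact binomial version has 73.7% power at 32.

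**2. Paired power at 32 LM patients.** By enumeration: discordant pairs M ~ Bin(32, psi), and OncoCEE-only pairs given M ~ Bin(M, (0.25 + s)/psi).

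| s (assumed) | psi | Exact McNemar | Mid-p | Uncorrected chi-square |
|---|---|---|---|---|
| 0% | 0.25 | 84.7% | 93.0% | 97.5% |
| 1% | 0.27 | 78.7% | 87.6% | 90.1% |
| 2.5% | 0.30 | 71.0% | 80.4% | 81.4% |
| 5% | 0.35 | 60.9% | 70.5% | 70.6% |
| 12.5% | 0.50 | 44% | 53% | 53% |

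The last row is independence within LM patients: s = 0.50 × 0.25 = 12.5%. The first row can be checked by hand. With s = 0 every discordant pair favours OncoCEE, and the three tests reject at 6, 5 and 4 or more such pairs. The Bin(32, 0.25) tails are 84.7%, 93.0% and 97.5%.

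The largest s that keeps 80% at 32 is about 0.8% (exact), 2.6% (mid-p) or 2.8% (chi-square).

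**3. Does the choice of test threaten the 5% level?** For total discordance of 0.20 to 0.35 at n = 32, type I error is 1.4 to 2.4% (exact), 3.3 to 4.2% (mid-p) and 4.3 to 4.7% (chi-square). The rejection regions are nested at every discordant count up to 36: exact lies within mid-p, and mid-p within chi-square. Picking the most favourable of the three after the fact is therefore the same as using chi-square, which stays below 5% over that range.

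**4. 36 against 32.** At s = 2.5%, n = 36 gives 78.3% (exact) and 85.7% (mid-p), against 71.0% and 80.4% at n = 32: differences of about 7 and 5 points. Under the plan's own assumptions, though, the 4 patients without LM are negative on both assays. They are concordant and add nothing to a McNemar test, so testing all 36 enrolled and testing the 32 with LM is the same test. The statement can be read as an enrolment figure with its expected LM yield.

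**5. A variable or smaller LM count.** With the count as Bin(36, 0.9), exact power is 85.1/71.6/61.5% at s = 0/2.5/5%, almost the same as at a fixed 32. At 31 LM patients, exact power is 82.4/68.9/59.0%: about 2 points lost per patient.

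**The case for a change.** The strongest case for a change is that nothing in the documents makes s small. OncoCEE works on a separate tube and identifies cells by cytokeratin staining; cytology is conventional microscopy; any solid tumor is eligible. At 75% sensitivity OncoCEE misses a quarter of LM patients, and s = 0 requires cytology to miss every one of them too. One or two cytology-only patients matter: 5% of 32 is 1.6 patients, and they take exact power from 85% to 61%. Section 2.1 makes the primary objective comparative, so the pilot label does not fully excuse an unexplained power claim. Stating the test and the share would cost a few sentences.

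Much of this stands. The 80% depends on an undeclared assumption, and the expected 32 is at the favourable end. What does not stand is the step from unstated to wrong. The steepest losses come from the exact test, whose actual error rate is less than half the nominal 5% over the range examined. The ordinary chi-square holds the 5% level there and still gives 81.4% at s = 2.5%. Nor could a stated value of s be anchored: no source in the documents gives one, so a 0 to 5% grid would put a reader's guess into the protocol. Section 8.1 already presents the 90% as anticipated, so labelling it an assumption adds nothing.

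**Conclusion.** No change to the plan follows. It is true that Section 8.1 and the Synopsis quote 80% for 36 patients, expect 32 with LM, and give neither a paired test nor a discordant share. This is missing detail, not a demonstrated miscalculation: the figures 32, 36 and 80% fit together under one simple derivation, and a standard paired test at 32 LM patients supports 80% for cytology-only shares up to about 2.6% (mid-p) or 2.8% (uncorrected chi-square).

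An analyst given paired first-puncture results would use a McNemar-type test among patients with LM without being told to. The data for it are collected under the plan as written, and the analysis would be valid whatever the discordance. The distinction between 36 and 32 disappears under the plan's own no-false-positive assumption.

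The limits should be kept in view. All values of s are assumptions. Power falls to 61 to 71% at a 5% share and to 44 to 53% if the assays are independent within LM patients. Fewer than 32 ever-positive patients would cost about 2 further points each (exact test). A non-significant result should therefore be judged by the discordant counts and the interval for the paired difference, as is usual for a pilot of this size.
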